Grade 3 = severe and undesirable adverse event.

Grade 4 = life-threatening or disabling adverse event.

Grade 5 = death.

All adverse events will be recorded and graded whether they are or are not related to disease progression or treatment. The NCI-CTCAE grades will be the primary source for scoring.

The relation, or attribution, of an adverse event to study participation will be determined by the investigator and recorded on CRF and/or SAE reporting form. The assignment of the causality should be made by the investigator responsible for the care of the participant using the definitions in the table below (Table 2). If any doubt about the causality exists the local investigator should inform the study coordination centre who will notify the Chief Investigators. The pharmaceutical companies and/or other clinicians may be asked to advise in some cases.

In the case of discrepant views on causality between the investigator and others, all parties will discuss the case. In the event that no agreement is made relating to a SUSAR, the MHRA will be informed of both points of view.

Table 2: Assignment of causality for adverse events

Relationship	Description
Unrelated	There is no evidence of any causal relationship
Unlikely	There is little evidence to suggest there is a causal relationship (e.g. the event did not occur within a reasonable time after administration of the trial medication). There is another reasonable explanation for the event (e.g. the participant's clinical condition, other concomitant treatment).
Possible	There is some evidence to suggest a causal relationship (e.g. because the event occurs within a reasonable time after administration of the trial medication). However, the influence of other factors may have contributed to the event (e.g. the participant's clinical condition, other concomitant treatments).
Probable	There is evidence to suggest a causal relationship and the influence of other factors is unlikely.
Definitely	There is clear evidence to suggest a causal relationship and other possible contributing factors can be ruled out.
Not assessable	There is insufficient or incomplete evidence to make a clinical judgement of the causal relationship.

GRADING AND ATTRIBUTION OF ADVERSE EVENTS: ALLERGIC REACTION

Allergic reactions to LAIV will be determined using the World Allergy Organisation (WAO) criteria for allergic reactions to immunotherapy, reproduced below. **For the purpose of this study**, mild symptoms of an allergic reaction (ie. non-anaphylactic symptoms) will be classified as non-serious adverse event, and should be documented on the CRF.

Any symptoms requiring treatment for anaphylaxis (adrenaline, steroids, salbutamol) **will be classified as a SERIOUS ADVERSE REACTION** and will be documented on both the CRF and a SAE form. The local investigator should also make a notification to the MHRA through the MHRA yellow card scheme.

On receipt of CRF / SAE forms, allergic reactions will be further classified by the ISC using World Allergy Organisation (WAO) criteria, which can be mapped to these grades and can be used to inform as to the appropriate NTI-CTCAE grade (Table 3).

Anaphylaxis will be defined as per the case definition and guidelines as described by the Brighton Collaboration Anaphylaxis Working Group (34) (see appendix 1).

WORLD ALLERGY ORGANISATION (WAO) GRADING SYSTEM FOR ALLERGIC REACTIONS TO IMMUNOTHERAPY

Grade 1	Grade 2	Grade 3	Grade 4	Grade 5

Symptom(s)/sign(s) of 1 organ system present*
 
Cutaneous Generalized pruritus, urticaria, flushing, or sensation of heat or warmth†
 
or
 
Angioedema (not laryngeal, tongue or uvular)
 
or
 
Upper respiratory Rhinitis - (eg, sneezing, rhinorrhea, nasal pruritus and/or nasal congestion)
 
or
 
Throat-clearing (itchy throat)
 
or
 
Cough perceived to originate in the upper airway, not the lung, larynx, or trachea
 
or
 
Conjunctival Erythema, pruritus or tearing
 
Other Nausea, metallic taste, or headache
	
Symptom(s)/sign(s) of more than 1 organ system present
 
or
 
Lower respiratory Asthma: cough, wheezing, shortness of breath (eg, less than 40% PEF or FEV₁ drop, responding to an inhaled bronchodilator)
 
or
 
Gastrointestinal Abdominal cramps, vomiting, or diarrhea
 
or
 
Other Uterine cramps
	
Lower respiratory Asthma (eg, 40% PEF or FEV₁ drop NOT responding to an inhaled bronchodilator)
 
or
 
Upper respiratory Laryngeal, uvula, or tongue edema with or without stridor
	
Lower or upper respiratory Respiratory failure with or without loss of consciousness
 
or
 
Cardiovascular Hypotension with or without loss of consciousness
	
Death

SERIOUS ADVERSE EVENT REPORTING

Serious adverse events and reactions must be reported to the PIs within 24 hours. An SAE/SUSAR form should be completed and faxed to the study coordination centre for all SAEs within 24 hours. This will then be communicated to the IDMC Chair, ISC chair and study sponsor. In the event of serious adverse reaction (expected), reporting should also include using the yellow card system.

In the case of suspected unexpected serious adverse reactions (SUSARS), the staff at the site should:

[figure not shown]
Complete the SAE case report form & send it immediately (within 24 hours, preferably by email or fax), signed and dated to the study coordination centre together with relevant treatment forms and anonymous copies of all relevant investigations.

Or

Contact the study coordination centre by phone and then send the completed SAE form to the study coordination centre within the following 24 hours as above.

The study coordination centre will notify the MHRA, REC and the Sponsor of all SUSARs occurring during the study according to the following timelines: fatal and life-threatening within 7 days of notification and non-life threatening within 15 days. All investigators will be informed of all SUSARs occurring throughout the study. Local investigators should report any SUSARs and /or SAEs as required by local requirements including the appropriate local Research & Development Office.

SUMMARY AND CONTACT DETAILS FOR REPORTING SAE AND SUSARS

Contact details for reporting SAEs and SUSARs:

[contact], attention [name]

Email: [contact]

STATISTICAL METHODS

SAMPLE SIZE ESTIMATION

Sample size is considered with respect to a historical comparison and also based on the precision around an estimate of 0%.

The SNIFFLE 1 study reported no systemic allergic reactions with 433 doses of LAIV administered to 282 egg-allergic children. On the basis of these data, the 95% upper confidence interval for occurrence of a significant allergic reaction to LAIV in egg-allergic children is <0.85%.

If, in a sample size of 730, there are no systemic or significant local allergic reactions, then this would provide confidence (at the 95% CI) that the true rate of allergic reaction to LAIV in egg-allergic children within the population is no more than 0.5%.

POPULATION TO BE ANALYSED

Children aged 2-17 years old with a physician-diagnosis of egg allergy as defined above.

STATISTICAL ANALYSIS PLAN

The incidence of reactions to LAIV (both immediate and delayed) will be estimated with 95% confidence intervals. Comparison to historical rates will be by Fisher's exact test. For the subgroup analyses, incidence of reactions will be compared between different cohorts (e.g. children with and without prior anaphylaxis to egg protein). Statistical differences will be determined using Fisher's exact test for proportions or using non-parametric tests for graded reactions. Sub-group analyses will be performed using the following criteria:

- Likelihood of clinical egg allergy (<95% and >95% likelihood)
- Severity of egg allergy
- Severe egg allergy – i.e. prior anaphylaxis to egg protein
- Baked egg tolerant
- Previous respiratory reactions to airborne egg
- Presence of physician-diagnosed asthma / recurrent wheeze
- Age: 2-5, 6-11, 12-17 years
- Children who have previously received influenza vaccine

INTERIM ANALYSIS

An interim analysis to assess the safety profile will be conducted after 100 participants have been recruited and received LAIV, the results of which will be reported to the IDMC Chair.

DATA MANAGEMENT

DATA COLLECTION

The following data will be collected:

- Patient demographics
- Current health to establish safety of immunisation
- Vaccination history:
 - previous exposure to influenza vaccine
 - previous reactions to vaccines
- Egg allergy:
 - Previous anaphylaxis? Tolerates baked egg? Respiratory symptoms to aerosolised egg?
 - Most severe reaction to egg: grading (WAO criteria)
 - Timing of most recent reaction
 - Recent diagnostic criteria: Skin test / serum specific IgE
 - Current egg avoidance
- Past medical history:
 - Medical indication for influenza vaccination or routine
 - Asthma: stable, uncontrolled
 - Active Allergic rhinitis
 - Current Medication including drug allergies
 - Other atopy: allergic rhinitis, eczema, other food allergies

Data will initially be submitted by a secure online data management system already used within Public Health England for vaccine surveillance. This data will be de-identified and accessible to the study team. Paper records kept locally at the study sites which will be identified by a study number.

DATA STORAGE

Paper records will be kept locally at the study sites which will be identified by a study number, within patient notes. De-identified patient data will be stored at the Immunisation Department, Public Health England and submitted to the study team using an online data management system.

De-identified study data will be kept for the statutory period and then disposed of securely. Local paperwork will be kept as part of the patient notes/CRF as per local policy.

ADMINISTRATIVE ASPECTS

ETHICAL COMPLIANCE

Approval will be sought from the West Midlands – Edgbaston National Research Ethics Committee. The study must be submitted for Site Specific Assessment (SSA) at each participating NHS Trust. The Study Coordination Centre will require a copy of the Trust R&D approval letter before accepting participants into the study. The study will be conducted in accordance with the recommendations for physicians involved in research on human subjects adopted by the 18th World Medical Assembly, Helsinki 1964 and later revisions

INFORMED CONSENT AND PARTICIPANT ASSENT

Consent to enter the study must be sought for each participant only after a full explanation has been given, an information leaflet offered and time allowed for consideration. Signed consent from the parent/legal guardian should be obtained. In children over 8 years of age, participant assent will also be sought. The right of the parent/guardian to refuse to participate without giving reasons must be respected. After the participant has entered the trial the clinician remains free to give alternative treatment to that specified in the protocol at any stage if he/she feels it is in the participant's best interest, but the reasons for doing so should be recorded. In these cases the participants remain within the study for the purposes of follow-up and data analysis. All participants are free to withdraw at any time from the protocol treatment without giving reasons and without prejudicing further treatment.

CONFIDENTIALITY

Participants' identification data will be required for the registration process. The Study Coordination Centre will preserve the confidentiality of participants taking part in the study and is registered under the Data Protection Act.

Email addresses for families will be entered into a secure encrypted online database managed by UK Department of Health through Public Health England. The email addresses will be destroyed at the termination of the study.

PROTOCOL ADHERENCE

Investigators ascertain they will apply due diligence to avoid protocol deviations. No unauthorized deviations are permitted. If the investigator feels a protocol deviation would improve the conduct of the study this must be considered a protocol amendment, and unless such an amendment is agreed upon by the ISC and approved by the ethics committee it cannot be implemented. All significant protocol deviations will be recorded and reported.

MODIFICATIONS OF THE PROTOCOL

Any change or addition to the protocol can only be made in a written protocol amendment that must be approved by the ISC and the ethics committee. Only amendments that are required for patient safety may be implemented prior to ethics approval. Notwithstanding the need for approval of formal protocol amendments, the investigator is expected to take any immediate action required for the safety of any patient included in this study, even if this action represents a deviation from the protocol. In such cases, The PIs should be notified of this action within 24 hours and the ethics committee should be informed within 10 working days.

FINANCIAL DISCLOSURE AND CONFLICTS OF INTEREST

The CIs declare no financial interests or conflicts of interest relating to this study.

USE OF DATA AND PUBLICATIONS POLICY

All publications and presentations relating to the study will be authorised by the Trial Management Group. The first publication of the trial results will be in the name of the Trial Management Group, if this does not conflict with the journal's policy. If there are named authors, these will include at least the trial's Chief Investigators, Statistician and Trial Coordinator, but not local PIs unless they have contributed to the writing of the manuscript. Members of the TMG and the Data Monitoring Committee will be listed and contributors will be cited by name if published in a journal where this does not conflict with the journal's policy. Authorship of parallel studies initiated outside of the Trial Management Group will be according to the individuals involved in the project but must acknowledge the contribution of the Trial Management Group and the Study Coordination Centre.

REFERENCES

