NUMBER OF SUBJECTS

- 730 children, on the basis of power calculations (see below).

EXPECTED DURATION OF STUDY

- Recruitment to commence 1st September 2014
- Clinical interventions to commence from mid-September 2014 for 5 months.

OUTCOME MEASURES

PRIMARY OUTCOMES:

- Immediate allergic reaction (occurring within 2 hours of administration)

SECONDARY OUTCOMES:

- Adverse events (of non-allergic aetiology) following administration
- Delayed onset allergic reaction (<72 hours following administration)
- Change in asthma control (by a validated questionnaire) pre and post LAIV

STUDY TREATMENT**DESCRIPTION**

Live Attenuated Intranasal Vaccine (Fluenz, Astra Zeneca), as provided for use by the Department of Health as part of the UK National Immunisation Schedule

At the current time, the Department of Health is planning to utilise the LAIV Quadrivalent vaccine (Fluenz Tetra, Astra Zeneca) for the influenza season 2014/15. However, in the event the quadrivalent LAIV is not available, vaccine supply will be with the trivalent LAIV.

DOSAGE AND ROUTE OF ADMINISTRATION

0.2 ml (administered as 0.1 ml per nostril). Immunisation must be carried out by nasal administration.

DOSE MODIFICATION

No dose modification proposed.

PREPARATION AND ADMINISTRATION OF STUDY DRUG

[figure not shown]
[figure not shown]
FLUENZ IS FOR NASAL USE only.

- DO NOT USE WITH A NEEDLE. Do not inject.

[figure not shown]

- FLUENZ is administered as a divided dose in both nostrils.
- After administering half of the dose in one nostril, administer the other half of the dose in the other nostril immediately or shortly thereafter.
- The patient can breathe normally while the vaccine is being administered – there is no need to actively inhale or sniff.
- Refer to the FLUENZ administration diagram (Figure 1) for step-by-step administration instructions.

[figure not shown]
Figure 1 FLUENZ Administration

[figure not shown]
1
Check expiry date
 Product must be used before date on applicator label.

[figure not shown]
2
Prepare the applicator
 Remove rubber tip protector. Do not remove dose-divider clip at the other end of the applicator.

[figure not shown]
3
Position the applicator
 With the patient in an upright position, place the tip just inside the nostril to ensure Fluenz is delivered into the nose.

4
Depress the plunger
 With a single motion, depress plunger as **rapidly as possible** until the dose-divider clip prevents you from going further.

5
Remove dose-divider clip

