NB: See Summary of Product Characteristics for full details of contra-indications to LAIV. Note that **Fluenz is not recommended during pregnancy. Administration of another live vaccine (e.g. MMR) within the previous 4 weeks is no longer a contra-indication to LAIV administration, according to updated DoH guidelines.**

Children requiring oral steroids for their asthma management (ie. BTS Step 5) may be included in the study if they meet the following criteria:

1. Their asthma is stable on their current regimen and has been so for the previous 2 weeks
2. They are reviewed by the centre PI prior to inclusion in the study
3. Their Asthma Control Test score at inclusion is no lower than 20.

SUBJECT WITHDRAWAL

The primary outcome in this study involves a single visit to a hospital for administration of the intranasal vaccine. Subsequent withdrawal will affect only the assessment of delayed symptoms, a secondary outcome measure, which will be collected by telephone.

TRIAL CLOSURE

The study will be considered complete following enrolment of the last patient and completion of the study procedures in that patient, or at the end of the influenza season 2014-15. Upon review by the ISC, recruitment may be extended if target recruitment is achieved prior to end of the influenza season and additional funding is available.

[figure not shown]
The study will be placed on hold and, upon review of study data and discussion with the IDMC, may be terminated early if any of the following occur:

- One patient suffers an allergic reaction that warrants admission to the ICU and use of mechanical ventilation
- Death of a participant during the study period, from any cause
- Two similar SUSARs (Suspected Unexpected Serious Adverse Reactions) or the repetition of one SUSAR

A teleconference will be scheduled within 72 hours if any of the aforementioned situations occur. This conference will be attended by the members of the IDMC and the ISC. At this teleconference the clinical relevance of the findings will be determined and recommendations may be made by the IDMC which may include:

- requesting further information
- modifying the protocol
- stopping enrolment
- institute more frequent monitoring guidelines
- termination of study

STUDY VISITS, PROCEDURES SCHEDULE and Patient Flow Diagram

	Visit 1	Phone follow up at 72 hours	Follow-up (by phone or email) after 4 weeks
Written Informed Consent (parent/ guardian)	X		
Written assent (child)	X		
Medical assessment	X		

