Asthma control questionnaire	X		
Vaccine administration followed by 30 mins observation	X		
Delayed effects telephone questionnaire at 72hrs		X	
Asthma control questionnaire at 4 weeks post LAIV in children with asthma/recurrent wheeze			X

Children who meet Department of Health criteria for specified ‘clinical risk categories’ (Table 3) and are under 9 years of age and have not received prior seasonal influenza vaccination in previous years will be offered a second dose of LAIV at least 4 weeks later. We expect very few children to meet the criteria for a second dose, as most would have received prior influenza vaccination. For example, using these criteria, no child enrolled in SNIFFLE 1 would have required a second dose. However, there is a duty of care to our participants and we are therefore including provision for a second dose in this protocol. Data pertaining to second visits will be collected on a separate CRF, but not used in the primary analysis.

Table 3: Clinical risk categories requiring a second dose of LAIV in vaccine-naïve children under age 9 years:

Chronic respiratory disease	
 • Asthma requiring continuous or repeated use of inhaled or systemic steroids or with previous exacerbations requiring hospital admission. • Chronic obstructive pulmonary disease (COPD) including chronic bronchitis and emphysema; bronchiectasis, cystic fibrosis, interstitial lung fibrosis, pneumoconiosis and bronchopulmonary dysplasia (BPD). • Children who have previously been admitted to hospital for lower respiratory tract disease.
Chronic heart disease	Congenital heart disease, hypertension with cardiac complications, chronic heart failure.
Chronic kidney disease	Chronic kidney disease at stage 3, 4 or 5, chronic kidney failure, nephrotic syndrome, kidney transplantation.
Chronic liver disease	Cirrhosis, biliary atresia, chronic hepatitis
Chronic neurological disease	Stroke, transient ischaemic attack (TIA). Conditions in which respiratory function may be compromised due to neurological disease (e.g. polio syndrome sufferers). Clinicians should consider on an individual basis the clinical needs of patients including individuals with cerebral palsy, multiple sclerosis and related or similar conditions; or hereditary and degenerative disease of the nervous system or muscles; or severe neurological or severe learning disability.

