- The intervention in this study is part of the routine UK National Immunisation Schedule. The study allows egg-children to participate in this programme in a safe environment, utilising a vaccine delivery route (intranasal) which minimises discomfort to the child. No procedures outside the normal vaccination process are planned.

TELEPHONE FOLLOW UP VISIT

Participants' families will be contacted by the local research team at least 72 hours after LAIV administration (and within 7 days, to allow for weekends), to determine whether their child has experienced any delayed symptoms which might be attributable to the vaccine. This telephone consultation will take approximately 2 minutes. A guide for this telephone call is provided in Appendix 2. These data will be recorded on the CRF. Following this, the CRF will be deemed complete and forwarded to the coordinating centre.

If after three attempts (on three separate days) the local study team is unable to contact the family, the child will be deemed lost to follow up and this will be documented on the CRF, which will then be closed.

ASTHMA CONTROL ASSESSMENT AFTER 4 WEEKS POST VACCINATION

Where the participant has a physician diagnosis of asthma or recurrent wheeze, the participants' families will be contacted 4 weeks after LAIV administration to determine their child's asthma control, using the same validated tool as at visit 1. Families will be asked at visit 1 as to whether they prefer to be contacted by telephone by the local study team, or receive an email request with a link to a secure, online survey. Either way, the survey will take 2-3 minutes to complete. A guide for the telephone call is provided in Appendix 3. These data will be recorded on a CRF, which will then be forwarded to the coordinating centre

If the family fails to respond to the email request, the local study team will attempt to contact the family by telephone. If, after three attempts (on three separate days), the local study team is unable to contact the family, the child will be deemed lost to follow up and this will be documented on the CRF, which will then be closed.

CLINICAL ASSESSMENTS

SKIN PRICK TESTING

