Existing data relating to skin prick testing to egg (where performed in routine clinical practice, according to BSACI guidelines (http://www.bsaci.org/Guidelines/Skin_Prick_Testing.pdf) and/or allergy blood tests (serum specific IgE to egg) will be collected from medical records, where available, to confirm sensitisation to egg.

No allergy testing will be performed as part of this protocol.

CLINICAL OBSERVATION / MONITORING OF PATIENTS BY CLINICAL STAFF

Patients will have baseline observations (temperature, heart rate, respiratory rate, oxygen saturations) performed prior to LAIV administration, with clinical respiratory and dermatological assessment at the same time.

Patients will be observed for at least 30 minutes after administration of LAIV, for symptoms of local or systemic allergic reaction. Symptoms (Total Nasal Symptom Score, TNSS) will be recorded at 10 and 30 minutes after vaccine administration, as follows:

Total nasal symptom score (TNSS)	
Rhinorrhoea	FOR EACH SYMPTOM, SCORE: 0 = no sign/symptom evident
Nasal congestion	1 = mild symptoms (sign/symptom clearly present, but minimal awareness; easily tolerated) 2 = moderate symptoms (definite awareness of sign/symptom that is bothersome but tolerable)
Nasal itch	3 = severe symptoms (sign/symptom that is hard to tolerate; causes interference with activities of daily living)
Sneezing	

[figure not shown]
US Department of Health and Human Services Food and Drug Administration, Allergic Rhinitis: Clinical Development Programs for Drug Products; 2000.
<http://www.fda.gov/downloads/Drugs/GuidanceComplianceRegulatoryInformation/Guidances/ucm071293.pdf>

Children will be observed in safe environment with appropriate clinical supervision and access to paediatric resuscitation facilities and trained staff, in the event of an anaphylactic reaction.

In the SNIFFLE study (2013/14 season), 8 children experienced possible local allergic symptoms following LAIV, all of which were mild and self-limiting. Symptoms commenced within 30 minutes of LAIV administration in all cases. Children will therefore be observed for 30 minutes, and if no symptoms are observed, discharged from the vaccine clinic. However, further clinical observations will be collected in the event of a clinical reaction, as per local policy.

TREATMENT OF ALLERGIC REACTIONS

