APPENDIX 2: TOPIC GUIDE FOR 72HR TELEPHONE FOLLOW-UP

Participants' families will be contacted by the local research team at least 72 hours after LAIV administration (and within 7 days, to allow for weekends), to determine whether their child has experienced any delayed symptoms which might be attributable to the vaccine. This telephone consultation will take approximately 2-3 minutes. If after three attempts (on three separate days) the local study team is unable to contact the family, the child will be deemed lost to follow up.

Guide to telephone interview:

1. Confirm interviewee's identity

2. Introduce yourself:

"I am <name>, from the SNIFFLE-2 Study. We arranged to speak briefly today to find how <participant's name> is going after his/her 'flu vaccine on <date>"

3. *"Have you noticed any health problems since the vaccine?"*

4. For each symptom reported:

- *When did this start?*
- *How long did this last?*
- *Did you do anything as a result?*

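### The 2-hour primary outcome is completed only by the 72-hour call for children discharged at 30 minutes, so the protocol is wrong that later withdrawal affects only a secondary outcome

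*Protocol*

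**What the plan says.** Outcome Measures gives one primary outcome: "Immediate allergic reaction (occurring within 2 hours of administration".

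Direct observation is shorter. The visit schedule lists "Vaccine administration followed by 30 mins observation". Clinical Observation / Monitoring sets the minimum, "Patients will be observed for at least 30 minutes after administration of LAIV", with nasal symptom scores at 10 and 30 minutes, and then the routine rule: "Children will therefore be observed for 30 minutes, and if no symptoms are observed, discharged from the vaccine clinic". Children who do react have further observations under local policy. No assessment at 2 hours is scheduled.

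The next planned contact is in Telephone Follow Up Visit, where families are "contacted by the local research team at least 72 hours after LAIV administration (and within 7 days, to allow for weekends". After three failed attempts on separate days, "the child will be deemed lost to follow up and this will be documented on the CRF". The script in Appendix 2 opens with "Have you noticed any health problems since the vaccine" and then, in item 4, asks for the start time and duration of each symptom reported.

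Subject Withdrawal ties the primary outcome to the single hospital visit and concludes: "Subsequent withdrawal will affect only the assessment of delayed symptoms, a secondary outcome measure, which will be collected by telephone".

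**The concern.** An allergic reaction that starts 60 minutes after the dose is a primary event by definition. If the child had no symptoms at 30 minutes, that child has normally gone home, and the only scheduled way to learn of the event is the call. The call therefore carries primary-outcome data, and a child lost before it has a primary outcome known for the first 30 minutes only. The withdrawal section says the opposite.

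Other parts of the protocol point the same way:

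- The schedule and the follow-up section describe the call as being about delayed effects only.
- The delayed-reaction outcome has an upper limit of 72 hours but no lower limit. A 60-minute reaction reported by telephone fits both outcome definitions and could be filed as secondary.
- The sample size section rests its 0.5% bound on all 730 children, with no allowance for children whose window is incomplete.

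If events are missed or misfiled, the error runs towards fewer primary events. That favours the conclusion the study is meant to inform, the safety of giving the vaccine in primary care.

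**Working it through.** **Inputs from the protocol**

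- Primary window: 0 to 120 minutes (Outcome Measures).
- Routine direct observation: 30 minutes (visit schedule; Clinical Observation / Monitoring).
- Next scheduled contact: 72 hours to 7 days (Telephone Follow Up Visit; Appendix 2).
- Sample size 730, zero events, stated bound 0.5% (Sample Size Estimation).
- Loss at the call: no rate is given. I assume 5%, 10% and 20%.

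**Share of the window without direct observation.** For a child symptom-free at 30 minutes: (120 − 30)/120 = 90/120 = 75%. This is clock time, not share of risk.

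**Reproducing the protocol's bounds.** The exact two-sided 95% upper limit with zero events in n is 1 − 0.025^(1/n).

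| n | Result | Protocol states |
|---|---|---|
| 282 children | 1.300% | under 1.3% |
| 433 doses | 0.848% | under 0.85% |
| 730 children | 0.504% | no more than 0.5% |

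The protocol's arithmetic is sound and uses the two-sided interval. A limit of exactly 0.5% needs ln(0.025)/ln(0.995) = 735.9, so 736 children. The planned 730 is close to that but leaves nothing spare.

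**Illustration with incomplete windows.** Leave out the children not reached and apply the same formula.

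| Not reached (assumed) | n covered to 2 hours | Zero-event upper limit |
|---|---|---|
| 0% | 730 | 0.504% |
| 5% | 694 | 0.530% |
| 10% | 657 | 0.560% |
| 20% | 584 | 0.630% |

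These limits are conservative, because leaving a child out also discards the 30 minutes that were observed.

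**One event.** If one qualifying reaction lay in the stretch seen only by telephone, the exact upper limit for 1/730 is 0.76%, against 0.504% if it were missed.

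**The reason given for 30 minutes.** The protocol cites 8 children in the preceding study, all with onset within 30 minutes. With 0 of 8 starting later, the two-sided upper limit for the share starting later is 1 − 0.025^(1/8) = 36.9% (one-sided, 1 − 0.05^(1/8) = 31.2%). Eight cases cannot exclude later onset.

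**The case against.** The strongest reply is that only one sentence is inaccurate and the rest is supposition. Much of this stands.

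- A reader might infer that the protocol tells the analyst to count unreached children as event-free. It does not. Population to be Analysed is defined by age and diagnosis and gives no rule for incomplete outcomes. Such a rule may sit in a statistical analysis plan that is not shown, and its absence is no finding. Loss at the call is recorded on the CRF, so a denominator of children covered to 2 hours could be built from planned data.
- A reader might also infer that the later 90 minutes are not ascertained at all. They are, in families reached: the opening question covers everything since the vaccine, and item 4 asks when each symptom began. The 75% means no direct observation, and only in children symptom-free at 30 minutes, since the 30 minutes is a minimum and reacting children are followed further. Serious events with onset within 72 hours are also to be collected.
- The 0.5% bound concerns systemic or significant local reactions, whereas the primary outcome is any immediate allergic reaction. The zero-event limits therefore illustrate the loss of information; they do not measure bias in the primary incidence.
- The 8 earlier cases were possible, mild, local symptoms. The 36.9% limit says little about the timing of systemic or significant reactions, and equally the 8 cases give little assurance about it.

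None of this rescues the withdrawal sentence. That the call asks for onset time confirms that it supplies part of the primary outcome.

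**Conclusion.** The contradiction is in the current text. For onset between 30 and 120 minutes, withdrawal or loss before the call leaves the primary outcome incomplete, and the protocol is wrong to say that only a secondary outcome is affected. This rests on the stated definitions alone.

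The consequence is conditional. If the sentence is followed and such children are kept as event-free, the incidence is biased towards zero. On assumed losses of 5% to 20%, the zero-event limit would be 0.53% to 0.63% in place of 0.504%: a modest shift, and an upper estimate of the precision lost. The documents do not show that the 0.5% calculation is wrong, or that many reactions would be missed. Nothing here bears on how long children should be observed.

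**What to change.** Reconcile Outcome Measures, Subject Withdrawal, the visit schedule, Telephone Follow Up Visit and Clinical Observation / Monitoring as follows:

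1. Correct Subject Withdrawal to say that withdrawal or loss before the call leaves the 2-hour primary outcome incomplete, and state in the follow-up section that the call completes it.
2. Classify a reaction reported by telephone with onset up to 2 hours as primary, using the onset time already asked in Appendix 2, item 4.
3. Report two incidences: 0–30 minutes in all vaccinated children, and 0–2 hours in children covered to 2 hours (still in clinic, or call completed). Add a sensitivity bound for those not reached.
4. Optionally, add a direct prompt about the first 2 hours to the existing call.

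No change to the clinical observation period is proposed. The cost is a few sentences and a slightly wider bound. The prompt, if wanted, has to be in place before calls are made, because that recall cannot be recovered later.
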